1. SYSTEM OVERVIEW

1.1 The iotaSOFT™ Insertion System is an electrode array insertion tool that assists cochlear implant (CI) surgeons to insert CI electrode arrays with consistent insertion speed and force. The system consists of a single-use, sterile drive unit connected to a reusable, non-sterile touch screen control console and footpedal interface (Figures 1, 2, & 3. See also Overview Video 1 and Attachment 1 Device Description). After standard mastoidectomy and facial recess approach for cochlear implantation, the surgeon secures the stage base to the skull at superior edge of mastoidectomy with two pre-loaded self-drilling bone screws (Figure 3). The drive unit is placed into the stage base and the adjustable drive head is coupled to a compatible CI electrode. Using manual manipulation, the drive unit head is positioned outside the facial recess and aligned to the surgeon-desired electrode array insertion trajectory. Before insertion begins, the surgeon selects the desired speed from 0.1mm/sec to 1.0mm/sec in 0.1mm/sec intervals. With direct access and view of the surgical site, the surgeon controls the electrode insertion forward and reverse motion via footpedal while guiding the electrode array into the cochlea with standard CI instrumentation as necessary. Upon the completion of electrode array insertion and securing the array at the cochlea, the drive head and unit are uncoupled from the electrode lead and removed from the patient for disposal. The surgical site is closed and CI procedure is completed in the standard fashion.

Figure 1. Photos of (Left) iotaSOFT™ Insertion System – Controller and Accessories with computer console, power supply, rolling stand, footpedal, and extension cables coiled on stand basket. (Right) iotaSOFT™ Drive Unit and screwdriver in sterile packaging tray after Tyvek cover and sterile tray cover removed.

[figure not shown]

Figure 2. Representative rendering of iotaSOFT™ Drive Unit with parts labelled.

[figure not shown]

Figure 3. iotaSOFT™ Drive Unit at edge of mastoidectomy during insertion into cadaveric cephalus (bottom) and computer render (top). (Left) iotaSOFT™ Drive Unit secured at edge of mastoidectomy and electrode engaged in drive head outside the facial recess as intended during use. (Right) Closer view of surgical site showing view of round window is not inhibited by device when in position.

2. BACKGROUND

2.1 360 million people worldwide, or 5% of the global population, have disabling hearing loss (>40 dB). Moderate to severe hearing loss affects 6.3 million patients in the US, yet only 5-6% of people who meet CI candidacy criteria receive a CI.¹ The number of patients that could benefit from a CI is expected to dramatically rise which makes improving patient access to CI interventions of the utmost importance.

2.2. Since the first description of “atraumatic” insertion techniques in 1993,² numerous studies have shown that trauma to the cochlea during electrode insertion results in damage to delicate inner ear structures, reduced implant performance, and the potential loss of residual hearing.³⁻⁷ While electrode array insertion technique has been shown to play a critical role in implant performance, the current standard of practice remains the use of manual forceps in which the inherent limitations of human kinematics makes slow and steady insertions difficult to achieve in a consistent manner.⁸ Alternatively, there are dedicated implant-specific manual insertion tools which have limited to no ability to precisely control the insertion speed or insertion force variability. Therefore, there is a clear need for an insertion tool that performs slow and steady insertions for a more standardized and controlled technique.

2.3. Studies evaluating the effect of electrode array insertion speed on insertion forces have shown that greater speeds directly correlate with greater intracochlear forces.^{9,10} Further, multiple studies demonstrate that high insertion forces damage the delicate structures of the cochlea, limiting CI performance and increasing the likelihood of the loss of residual hearing.¹¹⁻¹³ High insertion speeds have also been shown to increase the prevalence of intracochlear pressure spikes which can cause damage to the inner ear similar to loud noise exposure.¹⁴⁻¹⁶

2.4 Lastly, a clinical retrospective study evaluating CI recipients has shown that electrodes implanted at a “slow” manual speed (Average: 0.25mm/sec) experienced improved hearing preservation, decreased vestibular symptoms, and more complete electrode insertions compared to the “fast” speed (Average: 0.87 mm/sec).^{viii}

3. INTENDED/INDICATIONS FOR USE

3.1 The iotaSOFT™ Cochlear Implant Electrode Insertion System is intended to aid the surgeon in placement of cochlear implant electrode arrays into a radiographically normal cochlea by controlling the speed of implant insertion.

4. BENEFIT

4.1 The benefit of the iotaSOFT™ Insertion System is to provide the surgeon a standardized, more controlled, and consistent method of inserting the electrode array compared to manual insertion techniques. The system enables the surgeon to perform CI electrode array insertions more consistently and slowly than the capabilities of human motion. Literature shows consistent and slow insertions decrease the risk of additional hearing loss or vestibular symptoms from inherently uncontrolled, variable, and excessively forceful manual insertions.¹² The iotaSOFT™ Insertion System also provides consistency of electrode array insertions among different ENT surgeons, helping to ensure that each patient receives an

equally slow and consistent insertion regardless of the surgeon performing the procedure or the electrode array used.

4.2. Known risks associated with manual cochlear implantation (the current gold standard) include electrode translocation, electrode tip fold-over, incorrect placement of electrode array, loss of residual hearing, and/or vestibular symptoms. Currently, experienced CI surgeons mitigate these risks by performing slow and steady atraumatic CI insertion techniques by hand. The iotaSOFT™ insertion system enhances the surgeon's ability beyond the capability of human motion during the electrode insertion and therefore has the potential to reduce the current risk profile inherent in the standard CI surgical procedure.

4.3. Similarly, by giving each ENT surgeon more confidence in their ability to insert electrode arrays with less variability during CI surgery, the system has the potential to expand patient access for those with severe hearing loss in which less than 5% of eligible patients receive a CI.

5.0 RISK

5.1. The risk profile of the iotaSOFT™ Insertion System is predicated on the fact that the vast majority of the CI implantation procedure remains unchanged from manual CI insertion techniques. Likewise, the critical risks associated with use of the iotaSOFT™ Insertion System are also associated with manual insertion, meaning the iotaSOFT™ Insertion System does not add critical risk to the surgical procedure. Use of the device also does not prevent a surgeon from stopping at any time and immediately reverting to manual insertion techniques, and therefore the risk to the patient does not exceed the current gold standard of care. Nonetheless, all risks related specifically to the iotaSOFT™ Insertion System have been reduced to the lowest probabilities ($<10^{-5}$) and have been mitigated by device design verification and validation by iotaMotion. A list of all potential patient risks, their severity, and the mitigation steps taken is outlined in Table 1.

Table 1. Potential patient risks and mitigation actions

Potential Risk (Harm)	Severity	Mitigation Completed
Device fragments in patient	Serious	Device Functional Testing
Electric shock not resulting in death	Critical	Electrical Safety Testing
Environment Harm (Limited) - simple contamination, localized effects of short duration	Minor	Labeling
Inconvenience or temporary discomfort. Customer dissatisfaction where there is no injury.	Negligible	Electrical Safety Testing Labeling
Irritation / inflammation of surgical site (permanent)	Critical	Biocompatibility Testing
Patient or user infection or cross infection (biosafety)	Critical	Sterilization Testing Packaging Validation Device Functional Testing Usability Study

Prolonged operative/ anesthesia time due to delay during surgery	Minor	Device Functional Testing Labeling Usability Study Electrical Safety Testing
Prolonged operative/ anesthesia time due to delay during set up	Negligible	Electrical Safety Testing Electromagnetic Compatibility Testing Labeling
Temporary discomfort	Negligible	Device Functional Testing
Unintended thermal tissue damage; no intervention required	Minor	Electrical Safety Testing Device Functional Testing
Severity Rating		
Catastrophic	Results in patient death	
Critical	Results in permanent impairment or life-threatening injury	
Serious	Results in injury or impairment requiring professional medical intervention	
Minor	Results in temporary injury or impairment not requiring professional medical intervention	
Negligible	Inconvenience or temporary discomfort	

5.2. In addition to the testing listed as device-specific mitigations above, the device was evaluated against the current techniques to ensure no new risks (not listed above) were added by the use of the iotaSOFT™ Insertion System. The current known risks associated with manual cochlear implantation, including electrode translocation, electrode tip fold-over, incorrect placement of electrode array, loss of residual hearing, or vestibular symptoms, are currently attempted to be reduced by experienced CI surgeons performing slow and steady atraumatic CI insertion techniques by hand. The iotaSOFT™ insertion system enhances the surgeon's ability beyond the limits of human motion capabilities during CI insertions and therefore has the potential to reduce the current risk profile inherent in the standard CI surgical procedure. In summary, the risks associated with the iotaSOFT™ Insertion System have been successfully mitigated and are no worse than manual insertion. This conclusion was also supported by the results of the Cadaveric Comparative Analysis (see 6.1.3 Summary below and Attachment 4 for full report).

6 RISK MITIGATION – SUPPORTING DATA SUMMARY

6.1. As part of the overall risk mitigation, the iotaSOFT™ Insertion System was tested for functionality and safety in four categorical testing protocols and reports. Results are included in Attachments 2-5 and summarized briefly here.

6.1.1. **Bench Performance Testing Report (Attachment 2 – Doc #[contact])**

This report verified the functionality of the system according to design inputs following simulated transportation and distribution and accelerated aging. The specific device requirements that were tested include:

- 6.1.1.1. The device performs to the desired speed (selected between 0.1mm/s and 1.0mm/s) within 20%.

- 6.1.1.2.** The device can overcome electrode slip forces of at least 80mN.
- 6.1.1.3.** The device has maximum insertion forces and insertion force variation significantly less than the literature derived manual insertion forces and force variation, <300mN and ≤400mN/sec respectively.
- 6.1.1.4.** Forces imparted by the device during sheath removal following electrode insertion measured <100mN to ensure the device does not cause the electrode to dislodge during device removal.
- 6.1.1.5.** Forces imparted by the device on the electrode measured significantly less than the maximum pinch force a surgeon could impart on the electrode using a pad pinch and forceps.

6.1.2. Benchtop Comparative Analysis Report (Attachment 3 – Doc #[contact])

This engineering study compared the insertional force profiles obtained when inserting cochlear implant electrodes into synthetic cochleae using either manual technique or the iotaSOFT™ insertion system. Results showed that:

- 6.1.2.1.** The average insertion force variation for iotaSOFT™ driven electrode arrays was 78% lower than the average insertion force for manually inserted electrodes at 0.1mm/sec and 70% lower at 1.0mm.sec. These comparisons were both significantly different ($p\leq 0.007$).
- 6.1.2.2.** The average of maximum insertion force for iotaSOFT™ driven electrode arrays was significantly lower than average of maximum insertion force for manually driven electrodes ($p<0.05$); for both insertion rates, a 51% and 32% reduction at 0.1mm/sec and 1.0mm/sec, respectively, was observed.
- 6.1.2.3.** The iotaSOFT™ insertion system performed electrode array insertions with a lower variance of insertion force and force variation compared to manual surgeon insertions across surgeon skill levels. The total variance (cluster + residual) for the insertion force variation using the iotaSOFT™ assisted insertion was 186% and 190% lower than manual insertions for 0.1 and 1mm/sec respectively. Similarly, the maximum insertion force total variance for iotaSOFT™ assisted insertion was 190% and 188% lower compared to manual insertions across varying surgeon experience levels at both 0.1 and 1 mm/sec insertion rates, respectively.

6.1.3. Cadaveric Comparative Analysis Report (Attachment 4 – Doc #[contact])

This report evaluated the effect of the iotaSOFT insertion system on the final intracochlear electrode array position and electrode functionality compared to manual insertion of cochlear implant electrode arrays in cadaveric cochleae during simulated operative use. Results showed that:

- 6.1.3.1.** When compared directly to manual insertions, the iotaSOFT™ insertion system electrode insertions exhibited a lower percentage of intracochlear scala translocations, though the result was not statistically significant.
- 6.1.3.2.** A lower percentage of tip fold-overs was also observed with the iotaSOFT™ insertion system electrode insertions when compared to manual electrode insertions, though this result was also not statistically significant.

6.1.3.3 A lower percentage of tip fold-overs was also observed with the iotaSOFT™ insertion system electrode insertions when compared to manual electrode insertions, though this result was also not statistically significant.

6.1.4. Usability Validation Report (Attachment 5 – Doc #[contact])

The Usability Study assessed the occurrence of use errors related to the device. 16 ENT Surgeon/Nurse teams (in which the surgeons had completed a training session and training decay time) performed an CI implantation into a cadaveric cephalus in a simulated use environment. Test engineers observed insertions and noted any use errors, and user comments including a questionnaire and scoring table were collected. Results showed that:

6.1.4.1. Harms associated with the use errors found in the study were minor: prolonged operative/anesthesia time due to delay during surgery and prolonged operative/anesthesia time due to delay during set up. These minor potential harms were associated with use errors witnessed in a small percentage of users and tasks and were mitigated with a design change (eliminating the difficulties experienced with the device screwdriver) and updates to items emphasized in training. The residual use-related risk was minor and could not be further reduced with additional mitigations.

6.1.4.2. For all tasks, the use errors found could not lead to serious patient harm and no risk mitigations would lead to the reduction of overall or individual risks. The Usability results support that the iotaSOFT™ Insertion System is safe and effective for use by the intended users in a hospital setting. Surgeons can successfully use the iotaSOFT™ Insertion system to aid in placement of the electrode into the cochlea with nurse staff support.

7. CONCLUSION

The benefits of the device outweigh the minimal risks associated with the device. The iotaSOFT™ Insertion System provides the benefit of a 70% reduction in insertion force, 30% reduction in force variation (jerk), 180% reduction in variation between insertions with different surgeons or with different electrodes, and reduction in occurrence of electrode scala translocations and tip fold-over when compared to manual insertion. Furthermore, the iotaSOFT™ Insertion System is not statistically different than standard manual insertion techniques related to insertion angle, intracochlear scala position, and electrode electrical functionality. The risks associated with the device are not a significant clinical risk and are further mitigated by device completed design verification and validation testing as well as training provided to surgeons before the device can be used on patients.

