8.2.4 Post-Insertion Electrode Position X-ray Assessment

As per standard of care, following CI electrode array insertion, an intraoperative or post-operative “cochlea view” x-ray via c-arm will be performed to determine radiographically the insertion position of the electrode array and presence of tip-fold.

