9.1 Number of Sites and Subjects

Up to 30 subjects will be enrolled at up to 3 investigational sites. Each site will have adequate facilities for all medical procedures, and sites selected will represent private and larger medical center practice settings. All sites will be required to receive Institutional Review Board (IRB) approval prior to study initiation. Should clearance of the marketing application be received during the study, the Sponsor will determine whether to continue enrolling new subjects. Subjects already enrolled in the study who have not been implanted will be allowed to continue in the study.

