9.5 Exclusion criteria

The Subject must not have known or active medical issues that would preclude having a CI device, including:

- 1) Prior cochlear implantation in the ear to be implanted
- 2) Ossification or any other cochlear anomaly that might prevent complete insertion of the electrode array
- 3) Craniofacial abnormality or Abnormal cochlear/nerve anatomy on pre-operative CT or MRI imaging (excluding a mild Mondini malformation or Large Vestibular Aqueduct Syndrome)
- 4) Deafness due to lesions of the acoustic nerve or central auditory pathway
- 5) Diagnosis of auditory neuropathy
- 6) Active middle-ear infection
- 7) Additional handicaps that would prevent participation in evaluations
- 8) Unrealistic expectations on the part of the subject, regarding the possible benefits, risks and limitations that are inherent to the procedure and investigational device
- 9) Must not fit the definition of a vulnerable subject, as per FDA regulations 21 CFR Parts 50 and 56^{21,22}

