11. ADVERSE EVENTS

11.1 Definitions

An Adverse Event (AE) is any untoward medical occurrence in a study subject. This may include illness, sign(s), symptom(s), or clinically significant laboratory test abnormality that has appeared or worsened during the course of the study, regardless of causal relationship to the study device(s) under study.

A Serious Adverse Event (SAE) is any untoward medical occurrence that: results in death, is life-threatening (defined as an event in which the participant or patient was at risk of death at the time of the event; it does not refer to an event which hypothetically might have caused death if it were more severe), requires inpatient hospitalization or prolongation of existing hospitalization, results in persistent or significant disability/incapacity, is a congenital anomaly/birth defect, or is an important medical event (defined as a medical event(s) that may not be immediately life-threatening or result in death or hospitalization but, based upon appropriate medical and scientific judgment, may jeopardize the patient/participant or may require intervention (e.g., medical, surgical) to prevent one of the other serious outcomes listed in the definition above. Note: Planned hospitalization for a pre-existing condition without subsequent serious deterioration in health is not considered a serious adverse event.

An Adverse Device Effect (ADE) is any untoward or unintended response to a medical device.

(This includes any event resulting from insufficiencies or inadequacies in the instructions for use or the procedures related to the device.) This includes any AE that is determined to be definitely or probably a result of device use.

An Anticipated Adverse Device Effect (AADE) is an adverse device-related event that has been identified as to the nature, severity or incidence in the protocol.

An Unanticipated Adverse Device Effect (UADE) is any serious adverse effect on health or safety or any life-threatening problem or death caused by, or associated with, a device, if that effect, problem, or death was not previously identified in nature, severity, or degree of incidence in the investigational plan or application (including a supplementary plan or application), or any other unanticipated serious problem associated with a device that relates to the rights, safety, or welfare of subjects.

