11.3 Procedures for Reporting Adverse Events

Adverse events classified as "serious" or "unanticipated" (SAEs or UADEs) will be reported promptly to the IRB and study Sponsor to comply with regulatory requirements. All serious AEs, whether related or unrelated to the device, as well as all UADEs, will be immediately reported (but in no event later than 2 working days after the Investigator first learns of the event) to the Sponsor by telephone or confirmed facsimile or email transmission.

The Sponsor will immediately conduct an evaluation of any unanticipated adverse device effect. If the Sponsor determines that an unanticipated adverse device effect presents an unreasonable risk to subjects, the Sponsor will terminate all investigations or parts of investigations presenting that risk as soon as possible. Termination will occur not later than 5 working days after the sponsor makes this determination and not later than 15 working days after the sponsor first receives notice of the effect.

As required, the Sponsor will summarize all reported AEs that are serious, unexpected, and certainly, probably, possibly, or of undetermined relationship to the device. This information will be provided to the FDA (by the sponsor) and to the IRB by the Investigator or designee, as appropriate.

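### Do the overstated and mislabelled preclinical benefits in Section 7 affect how this trial is run or read?

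*Protocol*

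**What the plan says.** Section 7 closes the preclinical summary. It credits the device with a "70% reduction in insertion force, 30% reduction in force variation (jerk"), and then with a "180% reduction in variation between insertions with different surgeons or with different electrodes, and reduction in occurrence of electrode scala translocations and tip fold-over". Its next sentence says the device does not differ statistically from manual insertion on, among other things, scala position.

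The sources for that summary are in Section 6:
- 6.1.2.1: force variation 78% lower at 0.1 mm/sec and 70% lower at 1.0 mm/sec.
- 6.1.2.2: maximum insertion force 51% and 32% lower at the same speeds.
- 6.1.2.3: total variance 186% and 190% lower for force variation, and 190% and 188% lower for maximum force.
- 6.1.3: lower percentages of translocation and fold-over in cadavers, neither significant, with no counts given.

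The operational passages that might be affected are these:
- 11.1 defines an anticipated device effect as one "that has been identified as to the nature, severity or incidence in the protocol". An unanticipated one is serious and "not previously identified in nature, severity, or degree of incidence in the investigational plan or application".
- Under 11.3, if an unanticipated effect is judged an unreasonable risk, "the Sponsor will terminate all investigations or parts of investigations presenting that risk as soon as possible".
- Exclusion 8 in 9.5 concerns "Unrealistic expectations on the part of the subject, regarding the possible benefits, risks and limitations".
- 8.2.4 uses an X-ray "to determine radiographically the insertion position of the electrode array and presence of tip-fold".
- 9.1: "Up to 30 subjects will be enrolled at up to 3 investigational sites".

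**The concern.** Section 7 turns two non-significant cadaver differences into a stated benefit, attaches the bench percentages to the wrong quantities, and quotes a reduction above 100%. It is also the paragraph that concludes that benefit outweighs risk.

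Three routes could carry these errors into the trial:

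1. **Safety classification.** 11.1 mentions incidence identified in the protocol. For fold-over and translocation the protocol gives only a direction relative to manual insertion and no rate. If that direction is unsupported, a serious event might be put in the wrong class, and the 11.3 process follows from the class.
2. **Eligibility.** Exclusion 8 asks whether a candidate's expectations are realistic. Judged against Section 7, the yardstick would be wrong.
3. **Interpretation.** Fold-over is observed in at most 30 subjects with no comparator. A clean result might be read as confirming a reduction that the study cannot show.

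**Working it through.** **Step 1: bench figures (inputs from 6.1.2.1, 6.1.2.2 and Section 7).**

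| Quantity | 6.1.2 at 0.1 mm/sec | 6.1.2 at 1.0 mm/sec | Mean | Section 7 |
|---|---|---|---|---|
| Maximum insertion force | 51% | 32% | 41.5% | 70% |
| Force variation | 78% | 70% | 74% | 30% |

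As labelled, Section 7 matches no entry and neither mean. Force is overstated by 70 − 51 = 19 to 70 − 32 = 38 points. Force variation is understated by 70 − 30 = 40 to 78 − 30 = 48 points. With the labels exchanged, 70% is exactly force variation at 1.0 mm/sec, and 30% is close to the 32% for maximum force at that speed. This is the pattern of a labelling slip. The correct figures are all still reductions, and 6.1.2 reports both comparisons as significant.

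**Step 2: reductions above 100% (6.1.2.3 and Section 7).** With reduction = 1 − device/manual, a value of 186% to 190% puts the device variance at −86% to −90% of the manual variance, which is impossible. Two other formulas would produce such figures. Both are assumptions, because Attachment 3 is not shown.
- Symmetric difference d = 2(manual − device)/(manual + device), so device/manual = (2 − d)/(2 + d). For d = 1.86 this is 0.14/3.86 = 0.036, a reduction of 96.4%. For d = 1.88 it is 96.9%, and for d = 1.90 it is 97.4%. Section 7's 1.80 would be 94.7%.
- Manual higher by the stated percentage s, so reduction = 1 − 1/(1 + s). This gives 65.0%, 65.3% and 65.5%.

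Under either reading the device variance is well below the manual variance. The direction holds and the expression is wrong.

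**Step 3: safety classification.** 11.1 lists nature, severity and incidence as alternatives. Fold-over and translocation are named as known risks of manual implantation in 4.2 and 5.2, so they are identified in nature. The one incidence figure, below 10^-5 in 5.1, is for device-specific risks, and Table 1 lists neither event. Section 7 supplies no rate, so correcting or deleting its sentence leaves 11.1 exactly as usable as before. An unanticipated effect must also be serious, and termination under 11.3 needs a separate finding of unreasonable risk.

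**Step 4: eligibility.** Exclusion 8 does not cite Section 7. Under 10.1 and 13.2, candidates are informed through the consent form and a verbal explanation.

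**Step 5: what 30 subjects can show.** For 0 events in 30, the exact 95% upper limit is 1 − 0.05^(1/30) = 9.5% one-sided, or 1 − 0.025^(1/30) = 11.6% two-sided. For 1 in 30 (3.3%) the interval is 0.1% to 17.2%. The manual rate is not given. For assumed rates with no device effect, the probability of zero events is:
- 2%: 0.98^30 = 0.545
- 5%: 0.95^30 = 0.215
- 10%: 0.90^30 = 0.042

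A clean result would therefore be weak evidence of a reduction unless the manual rate were around 10% or more. In the other direction, 5 of 30 gives 5.6% to 34.7%, which excludes an assumed 5%, and 3 of 30 gives 2.1% to 26.5%, which excludes 2%. The study could reveal a clearly worse device. 8.1 states a safety purpose, and no comparison with manual insertion is proposed.

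**The case for a change.** The strongest argument for acting is that the errors can be read straight off the page and sit in the paragraph that justifies exposing subjects. They would also cost little to put right, from reports the sponsor already holds. A non-significant difference shows neither a reduction nor equivalence. So the benefit claim in Section 7 and the use in 5.2 of the same cadaver report to support a no-worse-than-manual conclusion both go beyond the data. The sentence on scala position in Section 7 sits awkwardly beside the claimed reduction in translocation.

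All of that stands as criticism of the text. It does not reach the conduct or analysis of the trial. The significance statement is given openly in 6.1.3, and 4.2 and 5.2 speak only of a potential to reduce risk, so a careful reader is not left without the facts. The force and force-variation reductions in 6.1.2 still point in favour of the device, so the benefit argument does not turn on the swapped labels. Adding a note to 8.1 that fold-over results are descriptive would only write down what a single-arm design already implies. Adding a rate to 11.1 would not repair anything that Section 7 breaks.

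**Conclusion.** Section 7 misreports its own sources: the force labels appear exchanged (19 to 38 points too high for force, 40 to 48 too low for force variation), a 180% reduction is impossible, and a qualifier on significance is lost. These are clerical and wording faults in preclinical background. None of the figures enters an eligibility rule, endpoint, sample size, analysis or stopping decision, and the links through 11.1, 11.3 and exclusion 8 do not hold when the passages are read together. The limits for 30 subjects are a caution for whoever reports the results, since zero events would not demonstrate a reduction. No change to the plan follows.

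This rests on the protocol alone. Attachments 3 and 4 and the consent form are not shown, so the formula behind the variance figures, the cadaver counts and what candidates are told cannot be checked. If the Section 7 claims had been carried into the consent form, that would be a matter for that document.
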